4.6.3.9. Injection Site Reactions

Injection site reactions, incidence, and related information reported via the “Injection Site Reactions” eCRF will be summarized by treatment. Information to be summarized includes the timing of the reaction relative to study drug administration, and characteristics of the injection site reaction: erythema, induration, pain, pruritis, and edema. Patient based and event-based summaries will be created.

Additionally, potential injection site reactions will be searched by pre-defined MedDRA HLTs of injection site reactions, administration site reactions, and infusion related reactions. Detailed searching criteria for injection site reaction events can be found in [Appendix 2](#) (Section 7.2). The PT will be used for summary by treatment within each HLT category.

4.6.3.10. Diabetic Retinopathy Complications

Results of the baseline dilated fundoscopic exam will be summarized by treatment and by visit at Baseline. A listing of unscheduled visits only will be provided. Any TEAE suspected of worsening retinopathy triggers a follow-up dilated fundoscopic exam. A summary of TEAEs suspected of worsening retinopathy and a summary of the results of the follow-up dilated

fundoscopic exam will be summarized by treatment and PT. The cases with repeated fundoscopy during the course of the trial, based on clinical suspicion of worsening retinopathy that have either findings of de novo retinopathy or progression of retinopathy, and severe/serious adverse events from the PTs defined in searching criteria in [Appendix 2](#) (Section 7.2) will be summarized.

4.6.3.11. Hepatic Safety

4.6.3.11.1. Hepatobiliary Disorders

The AE database will be searched using standardized MedDRA query SMQs to identify events consistent with hepatobiliary disorders. Detailed searching criteria can be found in [Appendix 2](#) (Section 7.2). A summary by treatment and PT within SMQ will be provided.

4.6.3.11.2. Acute Gallbladder Disease

The AE database will be searched using pre-defined SMQs to identify events consistent with acute gallbladder diseases. Detailed searching criteria for these AEs can be found in [Appendix 2](#) (Section 7.2). A summary by treatment and PT within SMQ will be provided.

4.6.3.11.3. Liver Enzymes

Analyses for laboratory analyte measurements are described in Section 4.6.4. This section describes additional analyses of liver enzymes. In addition, the following will be provided by treatment group:

- A shift table of maximum to maximum alanine aminotransferase (ALT) measurement from baseline ($\leq 1 \times \text{ULN}$, $> 1 \times \text{ULN}$) to postbaseline with the following categories: $\leq 1 \times \text{ULN}$, > 1 to $< 3 \times \text{ULN}$, ≥ 3 to $< 5 \times \text{ULN}$, ≥ 5 to $< 10 \times \text{ULN}$, $\geq 10 \times \text{ULN}$.
- A shift table of maximum to maximum aspartate transaminase (AST) measurement from baseline ($\leq 1 \times \text{ULN}$, $> 1 \times \text{ULN}$) to postbaseline with the following categories: $\leq 1 \times \text{ULN}$, > 1 to $< 3 \times \text{ULN}$, ≥ 3 to $< 5 \times \text{ULN}$, ≥ 5 to $< 10 \times \text{ULN}$, $\geq 10 \times \text{ULN}$.
- Shift tables of maximum to maximum total bilirubin and direct bilirubin from baseline to postbaseline with the following categories: $\leq 1 \times \text{ULN}$, > 1 to $< 2 \times \text{ULN}$, $\geq 2 \times \text{ULN}$.
- Shift tables of serum alkaline phosphatase from baseline to postbaseline with the following categories: $\leq 1 \times \text{ULN}$, > 1 to $< 2 \times \text{ULN}$, $\geq 2 \times \text{ULN}$.

Maximum baseline will be the maximum non-missing observation in the baseline period. The maximum postbaseline value will be the maximum non-missing value from the postbaseline period. Planned and unplanned measurements will be included.

4.6.3.12. Gastrointestinal Safety

The time courses of prevalence and incidence (newly-occurring episodes) of nausea, vomiting, diarrhea, and combined will be plotted by treatment and maximum severity.

The maximum severity and duration of treatment-emergent nausea, vomiting, diarrhea, and combined through the end of the study will be summarized by treatment.

The PTs in the gastrointestinal SOC will be used to identify gastrointestinal AEs. The incidence of the resulting TEAEs will be summarized by treatment and PT.

4.6.3.13. Acute Renal Events

Laboratory measures related to renal safety will be analyzed as specified for laboratory measurements in Section [4.6.3.13](#).

Two shift tables examining renal function will be created. A min-to-min shift table of eGFR estimated by the Chronic Kidney Disease Epidemiology Collaboration (CKD-EPI) equation with units mL/min/1.73m², using categories (<30, ≥30 to <45, ≥45 to <60, ≥60 to <90, and ≥90 mL/min/1.73m²). A max-to-max shift table of urine albumin-to-creatinine ratio (UACR), using the categories UACR <30 mg/g, 30 mg/g ≤ UACR ≤300 mg/g, UACR >300 mg/g (respectively, these represent normal, microalbuminuria, and macroalbuminuria).

The AE database will be searched using SMQs of acute renal failure and chronic kidney disease to identify events consistent with acute renal events. The incidence of the resulting TEAEs will be summarized by treatment and PT. Detailed searching criteria can be found in [Appendix 2](#) (Section [7.2](#)).

4.6.3.14. Dehydration

The AE database will be searched using SMQ of dehydration to identify events consistent with dehydration. Detailed searching criteria can be found in [Appendix 2](#) (Section [7.2](#)).

4.6.3.15. Metabolic Acidosis, Including Diabetic Ketoacidosis

The AE database will be searched using MedDRA PT to identify events consistent with metabolic acidosis, including diabetic ketoacidosis. Detailed searching criteria can be found in [Appendix 2](#) (Section [7.2](#)). The incidence of the resulting TEAEs will be summarized by treatment and PT.

4.6.3.16. Amputation/Peripheral Revascularization

The AE database will be searched using MedDRA PT to identify events consistent with amputation or peripheral revascularization. The incidence of the resulting TEAEs will be summarized by treatment and PT.

4.6.3.17. Major Depressive Disorder/Suicidal Ideation

The AE database will be searched using SMQs to identify events consistent with major depressive disorder or suicidal ideation. Detailed searching criteria can be found in [Appendix 2](#) (Section [7.2](#)). The incidence of the resulting TEAEs will be summarized by treatment and PT.

4.6.4. Vital Signs

Descriptive summaries by treatment and by nominal visit will be provided for baseline and postbaseline values as well as change from baseline values. If 2 records are taken at the same visit, they will be averaged prior to being used for data summaries and analyses.

An MMRM using REML model will be used to analyze the changes from baseline in vital signs at all scheduled postbaseline visits. The model will include baseline HbA1c (≤8.0%, >8.0%), treatment group, SGLT-2i use (Yes or No), visit, and treatment-by-visit interaction as fixed effects, and baseline value of the dependent variable as a covariate.

Counts and percentages of patients with treatment-emergent abnormal sitting systolic blood pressure (BP), sitting diastolic BP, and pulse will be presented by treatment. The criteria for identifying patients with treatment-emergent vital sign abnormalities are stated in [Table GPIM.4.3](#).

Table GPIM.4.3. Categorical Criteria for Abnormal Treatment-Emergent Blood Pressure and Pulse Measurements

Parameter	Low	High
Systolic BP (mm Hg) (Supine or sitting – forearm at heart level)	≤ 90 and decrease from baseline ≥ 20	≥ 140 and increase from baseline ≥ 20
Diastolic BP (mm Hg) (Supine or sitting – forearm at heart level)	≤ 50 and decrease from baseline ≥ 10	≥ 90 and increase from baseline ≥ 10
Pulse (bpm) (Supine or sitting)	<50 and decrease from baseline ≥ 15	>100 and increase from baseline ≥ 15

Abbreviations: BP = blood pressure; bpm = beats per minute.

4.6.5. Electrocardiogram

Summary statistics by treatment and by nominal visit will be provided for electrocardiogram (ECG) parameters (heart rate, PR, QRS, QT, and QT corrected using Fridericia's correction factor [QTcF]). When the QRS is prolonged (for example, a complete bundle branch block), QT and QTc should not be used to assess ventricular repolarization. Thus, for a particular ECG, the following will be set to missing (for analysis purposes) when QRS is ≥ 120 msec: QT and QTcF.

The criteria for identifying patients with treatment-emergent quantitative ECG abnormalities is outlined in [Table GPIM.4.4](#).

In addition, the percentage of patients with QT greater than 500 msec will be summarized, and the percentage of patients with QTcF greater than 500 msec will also be summarized (refer to PSAP).

The percentage of patients who experienced a treatment-emergent increase from baseline in QTcF interval of greater than 30 msec, 60 msec, or 75 msec at any time will be summarized. The maximum value during the study follow-up will be analyzed. Planned and unplanned measurements will be included.

Table GPIM.4.4. Selected Categorical Limits for ECG Data

Parameter	Low		High	
	Males	Females	Males	Females
Heart Rate (bpm)	<50 and decrease ≥ 15	<50 and decrease ≥ 15	>100 and increase ≥ 15	>100 and increase ≥ 15
PR Interval (msec)	<120	<120	≥ 220	≥ 220
QRS Interval (msec)	<60	<60	≥ 120	≥ 120
QTcF (msec)	<330	<340	>450	>470

Abbreviations: bpm = beats per minute; ECG = electrocardiogram; QTcF = Fridericia's corrected QT interval.

4.6.6. Clinical Laboratory Evaluation

All laboratory data will be reported in the International System of Units and Conventional Units. Values that are outside of reference ranges will be flagged as high (H) or low (L) in the listings. Descriptive summaries by treatment and by nominal visit will be provided for the baseline and postbaseline values as well as the change from baseline values for selected measurements.

Observed and change from baseline values for selected measurements for each visit will be displayed graphically for patients who have both a baseline and a postbaseline planned measurement. Unplanned measurements will be excluded from graphs.

Shift tables will be produced for selected measurements. A shift table will include unplanned measurements. The shift table will include the number and percentage of patients within each baseline category (low, normal, high, or missing) versus each postbaseline category (low, normal, high, or missing) by treatment. The proportion of patients shifted will be compared between treatments.

A listing of abnormal findings will be created for laboratory analyte measurements. The listing will include patient ID, treatment group, laboratory collection date, study day, analyte name, and analyte finding.

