9.3.6.4. Central Laboratory Measures, Vital Signs, and Electrocardiograms

Values and change from baseline to postbaseline values of central laboratory measures, vital signs, and selected ECG parameters will be summarized at each scheduled visit. The analysis model to make comparisons among treatment groups, relative to continuous change from baseline values assessed over time will be an MMRM similar to the primary efficacy analysis and with baseline measurement as a covariate. An unstructured covariance structure will model the relationship of within-patient errors.

The percentages of participants with TE abnormal, high, or low laboratory measures at any time will be summarized and compared between treatment groups by using Fisher's exact test. A TE abnormal value is defined as a change from normal value at baseline to a value greater than the high limit at any time during Periods II and III. A TE low result is defined as a change from a value greater than or equal to the low limit at baseline to a value less than the low limit at any time during Periods II and III. High and low laboratory limits will be determined by the central laboratory reference ranges.

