4.10. Changes to Protocol-Planned Analyses

NA

5. Sample Size Determination

Participants will be randomized in a 1:1:1:1 ratio to tirzepatide 5 mg, 10 mg, 15 mg, or placebo. The trial is powered to assess superiority of tirzepatide 10 mg and 15 mg, each tested in parallel, against placebo at a 2-sided significance level of 0.025, relative to the primary endpoint (mean change in HbA1c from baseline to 40 weeks), under the following assumptions: use of a 2-sample t-test utilizing HbA1c data collected before initiation of any rescue medication or premature treatment discontinuation with no more than 25% of participants initiating rescue medication or prematurely discontinuing treatment in each treatment group; 0.95% greater mean reduction in HbA1c from baseline for 10 and 15 mg tirzepatide compared with placebo; 1:1:1:1 randomization; and a common standard deviation (SD) of 1.3%. On the basis of these assumptions, a sample size of 256 participants is required to ensure at least 90% power to demonstrate that tirzepatide 10 mg and/or 15 mg are superior to placebo relative to the primary endpoint.

Assignment to treatment arms will be determined by a computer-generated random sequence using an interactive web response system (IWRS). Patients will be randomized in a 1:1:1:1 ratio to receive 5 mg tirzepatide, 10 mg tirzepatide, 15 mg tirzepatide, or placebo. The randomization will be stratified by baseline HbA1c concentration ($\leq 8.0\%$, $> 8.0\%$ [≤ 64 , > 64 mmol/mol]), and SGLT-2i use (Yes/No).

6. Supporting Documentation

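### SAP 4.6.6 drops the protocol's treatment-emergent high/low laboratory comparison and general MMRM without declaring it, and leaves an undefined comparison of patients 'shifted'

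*SAP*

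**What the plan says.** Protocol 9.3.6.4 commits to a directional comparison: "The percentages of participants with TE abnormal, high, or low laboratory measures at any time will be summarized and compared between treatment groups", by Fisher's exact test. It gives a definition for each direction. Upward: "A TE abnormal value is defined as a change from normal value at baseline to a value greater than the high limit". Downward: "A TE low result is defined as a change from a value greater than or equal to the low limit at baseline", to a value below that limit. Both apply at any time in Periods II and III. The same section plans an MMRM for change from baseline in central laboratory measures, vital signs and selected ECG parameters.

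SAP 4.6.6 plans by-visit descriptive summaries, graphs, high/low flags, a listing of abnormal findings and, for selected measurements, a shift table that counts patients "within each baseline category (low, normal, high, or missing) versus each postbaseline category (low, normal, high, or missing) by treatment". Unplanned measurements are included. It then says: "The proportion of patients shifted will be compared between treatments". It contains no TE high/low analysis and no MMRM. SAP 4.6.4 keeps the MMRM for vital signs. SAP 4.6.5 gives ECG summaries and categorical limits but no MMRM.

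SAP 4.10, the section for changes to protocol-planned analyses, reads NA.

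**The concern.** Someone programming from the SAP alone would not produce the comparison the protocol promises. They would also have to decide what counts as shifted: any change of category or only worsening; which postbaseline value sets the category (last, highest or lowest); whether 'missing' is a shift; and where to put a patient with both a low and a high postbaseline value. None of this is fixed before unblinding.

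On the plain reading, any move off the diagonal of a four-by-four table is a shift. High-to-normal, normal-to-high and normal-to-missing then carry the same weight. A difference between arms would not say which of these caused it, and a real excess of new abnormalities would be measured against a background of unrelated moves.

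**Working it through.** **Arm size.** The plan gives no figure for the laboratory comparison, so the only figure to reproduce is the arm size. Inputs from Protocol 9.5: difference 0.95, SD 1.3, two-sided alpha 0.025, 25% allowance. A two-sample t-test (noncentral t) with 48 evaluable per arm has 90.2% power. Then 48/(1 − 0.25) = 64 per arm and 4 × 64 = 256, as stated.

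**The texts compared.**
- Direction: defined upward and downward in Protocol 9.3.6.4; absent from SAP 4.6.6. The neighbouring SAP sections do give low and high criteria, for vital signs (Table GPIM.4.3) and ECG (Table GPIM.4.4).
- Test: Fisher's exact test in the protocol. SAP 4.1 makes it the default for categorical outcomes, so the test is not what is missing.
- Cross-references do not fill the gap. SAP 4.6.3.11.3 (liver) sends the reader to 4.6.4, which is vital signs; 4.6.3.13 (renal) refers to itself.

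**Dilution.** All rates here are assumptions. Let b be the share high at baseline (the rest normal), h the normal-to-high rate, r the high-to-normal rate and m the share moving to 'missing'.

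Literal shifted rate = (1 − m)[(1 − b)h + b·r] + m

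The directional test compares h among 64(1 − b)(1 − m) patients per arm. Take h = 25% on drug and 5% on placebo, with exact power of a two-sided 0.05 Fisher test.

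- b = 0, m = 0: the two tests coincide, at 87.4% power each.
- b = 30%, m = 0, r = 20% in both arms: shifted is 0.7 × 0.25 + 0.3 × 0.20 = 23.5% against 0.7 × 0.05 + 0.3 × 0.20 = 9.5%. Power is 48.8%, against 70.8% for the directional test (45 per arm).
- b = 0, m = 10% in both arms: shifted is 0.9 × 0.25 + 0.1 = 32.5% against 0.9 × 0.05 + 0.1 = 14.5%. Power is 60.5%, against 82.9% directional (58 per arm).
- b = 30%, m = 0, r = 10% on drug and 40% on placebo: shifted is 20.5% against 15.5%. Power is 7.5%, against 70.8%.

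**Same harm, different improvement.** Assumed counts: 64 per arm, 48 normal and 16 high at baseline, with 10 normal-to-high on tirzepatide and 2 on placebo. The directional comparison is 10/48 against 2/48, p = 0.027 (p = 0.030 if all 64 are the denominator).

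| High-to-normal, tirzepatide / placebo | Shifted, tirzepatide / placebo | Fisher p |
|---|---|---|
| 2 / 10 | 12/64 / 12/64 | 1.00 |
| 4 / 4 | 14/64 / 6/64 | 0.087 |
| 10 / 2 | 20/64 / 4/64 | 0.0005 |

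One directional finding gives three different answers, depending on moves that have nothing to do with harm.

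**The case against.** The strongest reply is that the SAP nowhere says improvement and 'missing' count as shifted, and nowhere withdraws the protocol analysis. The term could be read together with the protocol's directional definitions. That stands: the SAP omits the comparison and leaves a term undefined, and pooling is the literal reading rather than a stated rule.

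A reader might infer that benefit from tirzepatide would hide its harm. The documents do not support this, and the arithmetic runs the other way. In an undirected count, improvement on tirzepatide adds to its shifted total, as the last row of the table shows. Cancellation needs the opposite imbalance.

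A reader might also take the 25% in Protocol 9.5 to mean that 0.25 × 64 = 16 patients per arm could be 'missing'. That figure covers rescue or treatment discontinuation, not absent laboratory data. Rescued participants stay on randomized treatment and on the visit schedule (Protocol 8.3.4.2). Those who stop study drug are meant to complete all visits, and those who leave the study are to have an early discontinuation visit (Protocol 7.1).

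Much laboratory safety is covered elsewhere:
- pancreatic enzymes, by threshold tables and an MMRM (SAP 4.6.3.3.1);
- calcitonin thresholds (4.6.3.4.1);
- liver shift tables by multiples of the upper limit (4.6.3.11.3);
- minimum eGFR and maximum UACR shifts (4.6.3.13);
- models for lipids, UACR and eGFR (Tables GPIM.4.1 and GPIM.4.2).

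This stands and narrows the point. The threshold and shift tables, however, specify no between-arm test of those proportions. Finally, Protocol 9.3.1 and SAP 4.1 allow a non-principal change to be described in the clinical study report, so the SAP is not the only permitted place.

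**Conclusion.** The point holds in this form. The protocol's TE high/low comparison and its general MMRM for laboratory and selected ECG measures are missing from the SAP, and NA in 4.10 is inaccurate on this. The comparison left in 4.6.6 is undefined and, read literally, non-specific. It can dilute a directional signal: 71% to 49% power, or 83% to 60.5%, in the two cases with equal improvement or equal missingness in both arms. There is no loss if nobody is abnormal at baseline and nothing is missing. The size depends wholly on assumed rates and on the literal reading.

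The documents do not support saying that a laboratory harm would go unseen. Shift-table cells by arm, flags and listings would still show it. The exposure is mainly analytes without their own directional table or model: hematology, electrolytes, calcium, CK, uric acid and similar. The primary analysis, alpha and sample size are untouched. It should be corrected because a planned safety comparison has lapsed without comment.

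**What to change.** In SAP 4.6.6, replace the sentence on the proportion shifted with two separate comparisons per analyte, TE high and TE low. Use the Protocol 9.3.6.4 definitions at any time in Periods II and III, and compare each dose with placebo by Fisher's exact test. Take as denominator the participants at risk at baseline with at least one postbaseline value. The protocol states no denominator, so label this as a clarification added to it.

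Keep the shift tables descriptive, with 'missing' outside any test. Either restore the MMRM for laboratory and selected ECG measures, or record and justify its removal in SAP 4.10.

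The cost is SAP wording and standard output programming. No new data are needed and the sample size does not change.

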4.6.7. Device Product Complaints

A listing or a summary of all device product complaints, inclusive of device product complaints that lead to an AE or that could have led to an SAE had intervention not been taken will be provided. Additional summaries will be provided as deemed appropriate.

4.7. Other Analyses

4.7.1. Health Outcomes

The patient-reported outcome questionnaires will be completed by the patients at baseline and at 40 weeks (or early discontinuation visit prior to 40 weeks). Using ANCOVA analyses on EAS, p-values and 2-sided 95% CIs of health outcome measures described below will be derived and summarized for the 5 mg, 10 mg, and 15 mg doses of tirzepatide compared to placebo. No multiplicity adjustment will be made in the evaluation of health outcome measures. Item level missingness is dealt with as per the instrument developer's instruction.

4.7.1.1. Ability to Perform Physical Activities of Daily Living

A descriptive frequency table of individual items in APPADL questionnaire will be presented at baseline, observed endpoint, and endpoint including last observation carried forward (LOCF, exclude baseline observation). The changes from baseline to Week 40, with and without LOCF, of the raw and transformed total APPADL scores will be analyzed using an ANCOVA model with model terms of treatment, baseline HbA1c ($\leq 8.0\%$, $> 8.0\%$ [≤ 64 , > 64 mmol/mol]) and SGLT-2i use (Yes or No) as fixed effects, and corresponding baseline APPADL score as a covariate.

4.7.1.2. Impact of Weight on Self-Perceptions Questionnaire

A descriptive frequency table of individual items in IW-SP questionnaire will be presented at baseline, observed endpoint, and endpoint including last observation carried forward (LOCF, exclude baseline observation). The changes from baseline to Week 40, with and without LOCF, of the raw and transformed total IW-SP scores will be analyzed using an ANCOVA model with model terms of treatment, , baseline HbA1c ($\leq 8.0\%$, $>8.0\%$ [≤ 64 , >64 mmol/mol]) and SGLT-2i use (Yes or No) as fixed effects, and corresponding baseline IW-SP score as a covariate.

